#### **4.4.2 Data Collection and Follow-up for Withdrawn Subjects or Lost to Follow-Up Subjects**

If a subject withdraws consent to participate in the study, we will attempt to obtain permission to record at least survival data up to the protocol-described end of subject follow-up period. We will also seek permission to record the full data set on such subjects to fully support the analysis. At the time the subject consents to participating in the study, we will obtain their permission to contact additional sources as described below in the event we are unable to collect survival data from the subject. Methods to contact subjects will include, if possible, several phone calls on different days of the week and time of day, calls to next of kin, communication with community peer supports (case-worker, case manager, housing outreach personnel, etc.), electronic messaging, and certified letters. We will also use locator information available in health records, (e.g. Bellevue Hospital Medical Record, New York City Department of Homeless Services outreach data, New York City Fire Department and Emergency Medical Services transport data). We will track mortality data through vital statistics for subjects who are lost to follow up.

### **5 Study Drug**

#### **5.1 Description**

Extended-release naltrexone (XR-NTX) 380mg (4 mL) will be administered as an intramuscular gluteal injection. Naltrexone is an opioid antagonist with little, if any, opioid agonist activity. This study will use an extended-release depot form of naltrexone (XR-NTX, Vivitrol®) that is FDA-approved treatment for alcohol dependence. XR-NTX is supplied as a microsphere formulation of naltrexone for suspension, to be administered by intramuscular injection. The microspheres consist of a sterile, off-white to light tan powder that is available in a dosage strength of 380 mg naltrexone per vial. The microspheres will be suspended in a clear, colorless diluent (polylactide-co-glycolide) prior to injection.

#### **Pharmacodynamics/Kinetics**

Duration: I.M.: 4 weeks

Distribution:  $V_d$ : ~1350 L; widely throughout the body but considerable inter-individual variation exists

Metabolism: Extensively metabolized via noncytochrome-mediated dehydrogenase conversion to 6-beta-naltrexol (primary metabolite) and related minor metabolites; glucuronide conjugates are also formed from naltrexone and its metabolites

Protein binding: 21%

Half-life elimination: I.M.: naltrexone and 6-beta-naltrexol: 5-10 days

Time to peak, I.M.: Biphasic: ~2 hours (first peak), ~2-3 days (second peak)

Excretion: Primarily urine (as metabolites and small amounts of unchanged drug)

#### **5.2 Treatment Regimen**

Extended-release naltrexone (XR-NTX) dose at 380mg (4 mL) will be administered as an intramuscular gluteal injection every 3 to 4 weeks for a total of as many as 12 doses. XR-NTX administration will be planned to occur every 28 days, but XR-NTX may be given as early as every 21 days depending on subject's clinical response and scheduling needs, which is consistent with usual clinical care. We will plan for each subject to receive 6 months of medication and will explore continuing treatment for up to 12 months of XR-NTX.

The duration of XR-NTX has not been established. We expect this population having a severe form of AUD may benefit from a longer duration of treatment.

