## Study Summary

Title	Novel Interventions for Alcohol Dependent Frequent Emergency Department Users: A phase IV, randomized, open-label, non-placebo-controlled, single-center study of the feasibility, acceptability, and effect of extended-release naltrexone 380mg intramuscular injection compared to standard care on healthcare utilization, drinking, and quality of life in subjects with severe alcohol use disorders and frequent emergency department use.
Short Title	XR-NTX in ED users with AUDs
Protocol Number	S13-00928
Phase	4
Methodology	Randomized, Open Label, non-placebo (compared to standard care)
Study Duration	8 years
Study Center(s)	Single-center
Objectives	To conduct a feasibility and acceptability study of XR-NTX+CM treatment in alcohol dependent patients with frequent ED use and explore its effect on healthcare utilization, drinking, and quality of life.
Number of Subjects	300 (Pilot, N=50; Subsequent trial N=250)
Diagnosis and Main Inclusion Criteria	Alcohol use disorder and frequent emergency department use
Study Product, Dose, Route, Regimen	Extended-release naltrexone (Vivitrol) 380mg intramuscular injection every 4 weeks
Duration of administration	12 months
Reference therapy	Reference is treatment as usual (No medications)
Statistical Methodology	Formal statistical analysis is not planned for the primary aim, in which we will a) further develop and pilot procedures and b) descriptively document feasibility and acceptability of XR-NTX for frequent ED users with alcohol use disorders. To explore the intervention effect, we will generate descriptive statistics and calculate changes in scores within and between groups.

CONFIDENTIAL

This material is the property of the NYU School of Medicine and Langone Medical Center. Do not disclose or use except as authorized in writing by the study sponsor

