## 1.5 Dose Rationale

XR-NTX 380mg intramuscular injection every 4 weeks is the FDA approved and recommended dosage for the treatment of alcohol dependence. We will administer XR-NTX according to these guidelines. As per the above data, the extended release preparation is favorable to the oral formulation because it helps address non-adherence. The dosage of XR-NTX 380mg has demonstrated the best efficacy while maintaining safety. The treatment duration is variable in research and clinical practice; the minimum duration is typically 3 months. Duration is generally extended in patients with more severe or refractory alcohol dependence, such as the patients we will be studying. We will plan for each subject to receive 6 months of medication and will explore continuing treatment for up to 12 months of XR-NTX.

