in the study may be intoxicated from alcohol when they arrive in the emergency department, but will not be enrolled until medically stable and clinically sober. Patients (potential subjects) may be placed into ED observation for the extended duration of care necessary to achieve this state. If this represents a minor deviation from the VIVITROL labeling, it may affect efficacy but should not represent an additional safety concern. XR-NTX is not aversive therapy and does not cause a disulfiram-like reaction as a result of ethanol ingestion. XR-NTX has been shown to be safe and effective among both individuals who are abstinent and actively drinking. A subject's ability to abstain from drinking prior to an initial XR-NTX injection may predict treatment response. However, this association has not been seen in all studies, including an XR-NTX pilot conducted in Bellevue Hospital primary care. Further, the administration of XR-NTX for the treatment of alcohol dependence users in this study is consistent with current clinical care for alcohol dependent patients in other clinical settings, including Bellevue Hospital Ambulatory care. The administration of XR-NTX in our protocol is based on protocols of ongoing studies of XR-NTX for alcohol dependence in other clinical and community settings, including [name] XR-NTX study in Bellevue Hospital ambulatory care (R01AA020836; S12-02263) and [name]' study in a Seattle community housing program (R01 AA022309), which the FDA also determined was exempt from IND reporting. Also of note, the investigation is not intended to be reported to FDA as a well-controlled study in support of a new indication and there is no intent to use it to support any other significant change in the labeling or advertising of the drug. The investigation does not involve a route of administration, dose, patient population, or other factor that significantly increases the risk associated with the use of the drug product.

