**Intervention Arm:**

1. PI will administer XR-NTX 380mg as an intramuscular gluteal injection (after urine drug screen is confirmed to be negative for opioids).
2. PI/RA will facilitate a harm-reduction based motivational interview and psychosocial assessment with the social worker or care manager (if available) that focuses on harm reduction and identification of subjects' goals and needs to inform ongoing care management plan. PI will train future staff. See therapy manual - Attachment #3. Subjects' healthcare, housing, and social assistance will be coordinated through the CM model.
3. Notify homeless services outreach of subject if homeless. Subject will be assigned a homeless outreach case worker and be offered shelter if eligible.
4. Provide referral to Bellevue Chemical Dependency clinic (or a suitable alternative) for ongoing alcohol-medical management. Subjects will be navigated directly to the clinic on their enrollment visit if possible. Subjects will receive a one-week referral to Bellevue ambulatory care for initial Alcohol-Medical Management (MM) and will also be scheduled every 4 weeks (or after most recent XR-NTX injection) for MM and XR-NTX injections (for a total of up to 12 injections).
5. Provide card containing the PI's contact information, dates of XR-NTX administration, and relevant medication information for medical personnel.

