At these meetings, [name] and other research personnel will report on the trial status, followed by a closed session under the direction of the DSMB chairperson, during which time the investigators and research team may be present. This will be followed by an executive session restricted to DSMB members. Issues discussed may include those related to subject safety and benefit, whether the primary study question is being answered, conflict of interest, confidentiality, and ongoing study review (including AEs, SAEs, and regulatory issues).

All adverse events and unanticipated problems during follow-up will be reported to the IRB, DSMB, and NIAAA. Serious adverse events and unanticipated problems will be reported to the IRB and to the NIAAA project officer within 48 hours of it becoming known to the investigator, using the appropriate forms found on the website. The PI and DSMB will conduct a review of all adverse events upon completion of study subjects. The PI will evaluate the frequency and severity of the adverse events and determine if modifications to the protocol or consent form are required.

During the review process, the DSMB will evaluate whether the study should continue unchanged, require modification/amendment, continue or close to enrollment. Either the principal investigator, DSMB, or the NYU IRB have the authority to stop or suspend the study or require modifications. Following each DSMB meeting, recommendations will be made by the chairperson to [name] and a final report (edited by all DSMB members) will be prepared and submitted to NIAAA, the NYUMC IRB, and (if required) the FDA.

Stopping the trial due to safety concerns or interim analysis of the primary outcome are not anticipated; the study medication, XR-NTX, is FDA-approved, its use in this trial is consistent with its FDA labeling, and no significant safety issues have arisen in national post-marketing use. DSM Plans typically include stopping rules that specify the outcome differences detected between groups during an interim analysis that can result in stopping the clinical trial. In general, stopping rules will reflect one of the following conditions: 1) there is clear evidence of harm or harmful side-effects of the treatment; 2) there is not

CONFIDENTIAL

This material is the property of the NYU School of Medicine and Langone Medical Center. Do not disclose or use except as authorized in writing by the study sponsor

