Extensive provisions are incorporated in the study protocol to ensure adequate protections of the subjects, all of who are considered to be vulnerable. No persons who are prisoners will be eligible for enrollment. In other words, all subjects will be entering the study as non-prisoners. Thus, there is no risk of coercion of prisoners to enroll/participate in the study. All patients will have a rigorous assessment of their capacity to consent to research participation, as described in section 4.3.3. The risks involved in the research are commensurate with the risks that would be accepted by non-prisoner volunteers. There are no added safety risks should subjects become prisoners. No additional advantages accruing to a prisoner through his/her participation in the research are of such magnitude that his/her ability to weigh the risks and benefits of the research will be impaired.

As medication (XR-NTX) is being administered in this study, it is important to explicitly state that there are no additional safety concerns for subjects in the arm receiving medications should they become prisoners. This FDA-approved medication is being administered in accordance with its safe prescribing guidelines. We do not anticipate that administration of XR-NTX will be disrupted as a result of incarceration; this is because Bellevue Hospital has an existing clinic dedicated to the care of prisoners (mostly from Rikers Jail). Protocols for the transfer of prisoners from detention centers to Bellevue Hospital for clinical care have existed many years. Subjects who are prisoners will return to Bellevue Hospital for their medical management, which may include laboratory testing and XR-NTX administration. XR-NTX is not administered unless the requisite pre-administration laboratory testing is completed. Thus, if the subject is unable to return to our medical clinics for medical management and laboratory testing, then the subject will not receive the subsequent dosage of XR-NTX. There are no adverse effects associated with disrupted treatment (other than the lack of benefit provided by the medication); XR-NTX may be discontinued at any time.

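### Section 5.2 permits injections only 21 days apart, an interval that the protocol's label-based safety statements do not cover

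*Combined protocol and SAP*

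**What the plan says.** Section 5.2 sets the regimen at 380 mg "every 3 to 4 weeks for a total of as many as 12 doses". It names 28 days as the planned interval and then states that "XR-NTX may be given as early as every 21 days depending on subject's clinical response and scheduling needs". Its support for the shorter interval is usual practice; it does not say that the interval is within the label.

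Elsewhere the regimen is 4-weekly:

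- Study Summary: "Extended-release naltrexone (Vivitrol) 380mg intramuscular injection every 4 weeks", with no shorter option.
- Section 1.5: "XR-NTX 380mg intramuscular injection every 4 weeks is the FDA approved and recommended dosage for the treatment of alcohol dependence", followed by a commitment to dose accordingly.
- Section 1.2 (Absorption): the product is described as designed for 4-weekly or monthly injection.
- Section 3.1: injections at weeks 4 to 24, with possible further ones at weeks 28 to 44, scheduled 4 weeks after the latest injection.
- Section 6.1, intervention arm: subjects "will also be scheduled every 4 weeks (or after most recent XR-NTX injection) for MM and XR-NTX injections".

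Four sections describe use by reference to the label or approved dosage. Section 5.4 says the approved dosage will be used. Section 8.6.1 says that "its use in this trial is consistent with its FDA labeling", as one reason why stopping for safety is not expected, and section 10.1 repeats this. Section 13 says: "This FDA-approved medication is being administered in accordance with its safe prescribing guidelines".

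Section 1.6.1 concedes that use may depart slightly from the label, but the departure it discusses is sobriety and abstinence before injection. It then states: "The investigation does not involve a route of administration, dose, patient population, or other factor that significantly increases the risk associated with" use of the product.

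**The concern.** By the protocol's own definition in section 1.5, the approved dosage includes the 4-week interval. A 21-day interval is therefore not the dosage that sections 5.4, 8.6.1, 10.1 and 13 refer to. An IRB or DSMB member who relies on those sections, or on the Study Summary, would not learn that a shorter interval is allowed.

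This matters most in sections 8.6.1 and 10.1, where label consistency helps to justify not expecting to stop for safety. Section 8.6.1 also plans no interim analysis of safety data. With no formal interim look, the description of the regimen that the monitors are given has to be accurate.

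There is a smaller wording problem. Section 3.1 counts 4 weeks from the latest injection. Section 6.1 inserts the word ‘or’, so that its alternative states no interval at all. The visit texts in sections 6.3 to 6.13 order an injection at each scheduled week without referring to either rule.

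**Working it through.** **Inputs.** Dose 380 mg; planned interval 28 days; shortest permitted interval 21 days; cap of 12 doses (all section 5.2). Injection visits at week 0 and weeks 4 to 44 (section 3.1).

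**1. The plan's own figure.** Injections at weeks 0, 4, 8, …, 44 number 44/4 + 1 = 12. The 12-dose cap is thus reproduced exactly by the 4-weekly schedule.

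**2. Dose rate** (dose divided by interval).

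- 28 days: 380/28 = 13.6 mg/day (95.0 mg/week).
- 21 days: 380/21 = 18.1 mg/day (126.7 mg/week).
- Ratio: 28/21 = 1.33, or 33% higher.

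**3. Injections through week 24, counting week 0.**

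- 4-weekly: 24/4 + 1 = 7.
- 3-weekly: 24/3 + 1 = 9.

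**4. Timing of the 12th dose** (11 intervals after the first).

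- 28 days: 11 × 28 = day 308, week 44.
- 21 days: 11 × 21 = day 231, week 33.

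**5. Maximum total dose.** 12 × 380 = 4,560 mg under either interval. The rate changes; the ceiling on the total does not.

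**6. The texts side by side.**

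| Place | Interval or claim | Mentions 21 days? |
|---|---|---|
| Study Summary | 4 weeks | No |
| 1.5 | 4 weeks, named as the approved dosage | No |
| 1.6.1 | Slight label departure conceded; abstinence discussed | No |
| 3.1 | 4 weeks from the latest injection | No |
| 5.2 | 28 days planned, 21 days permitted | Yes |
| 5.4 | Approved dosage | No |
| 6.1 | 4 weeks, or after the latest injection | No |
| 8.6.1, 10.1 | Consistent with labelling | No |
| 13 | Follows prescribing guidelines | No |

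Sections 5.4, 8.6.1, 10.1 and 13 state no interval themselves. Their link to 4 weeks runs through section 1.5, which supplies the protocol's only definition of the approved dosage.

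**The case against.** The other side has real points.

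- **The 33% is a ceiling.** It needs every dose at exactly 21 days. Section 5.2 plans 28 days, and sections 3.1, 4.4.1 and 6 expect missed and late visits. This stands, and the figure should be read only as the limit of what is permitted.
- **The shorter interval is not hidden.** Section 5.2 is part of the protocol that the IRB approves and the DSMB reviews at the outset, and section 1.6.1 says that the FDA reviewed the protocol and admits a possible slight label departure. This also stands, although the version the FDA saw is not stated. It answers any suggestion of concealment, but it does not make the label statements agree with section 5.2.
- **Section 1.6.1 is worded carefully.** It denies only a significant increase in risk, and the documents do not contradict that. It is the weakest of the supports.

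A reader might also infer that the visit texts order a dose 14 days after a late one, for example at week 8 after a week-4 dose given at week 6. They do not, when read with the rest: section 3.1 counts from the latest injection, section 5.2 sets 21 days as the minimum, and section 6 calls the visit procedures ideal conditions. What remains is a missing cross-reference.

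Nor does allowing timing to follow clinical response bias the comparison of arms. That comparison is of all randomized subjects by intention to treat (sections 7.2.2 and 7.3), and how best to give the drug is itself part of the primary aim.

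**Conclusion.** The contradiction holds. Section 5.2 cannot stand beside the Study Summary and section 1.5 as written, and the statements in sections 5.4, 8.6.1, 10.1 and 13 do not cover the whole of the permitted regimen. The size, at the limit, is a dose rate one third higher, two more injections through week 24, and the cap reached 11 weeks sooner. This rests on two readings: that section 1.5 defines what the protocol means by approved dosage, and that a subject could receive every dose at the minimum interval.

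Three stronger conclusions are not supported.

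- **That 21-day dosing is unsafe.** No passage shows this, and the point does not need it.
- **That drug accumulation can be estimated from the quoted half-life.** A one-compartment calculation at the upper half-life of 10 days gives 1/(1 − 2^(−28/10)) − 1 = 16.8% at 28 days, above the figure of under 15% in section 1.2. The model does not reproduce the documents' own value, so it should not be used for 21 days.
- **That the shorter interval spoils the week-48 assessment.** A planned 6-month course with its last dose at week 24, and 4 weeks of cover per dose (section 5.1), already leaves 48 − 28 = 20 weeks without cover.

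The sample size is not affected.

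**What to change.** 1. Reconcile the Study Summary and sections 1.5, 3.1, 5.2 and 6.1 to one interval rule with one anchor, and have sections 6.3 to 6.13 refer to it. The choice belongs to the responsible clinicians and regulators; this review takes no position on it.
2. If any interval other than the one in section 1.5 is kept, qualify the statements in sections 1.6.1, 5.4, 8.6.1, 10.1 and 13, and tell the IRB and the DSMB.
3. Derive the actual interval from injection dates already recorded: section 6.1 puts them on the subject's card, and section 7.2.1 extracts the administration notes. Add the reason for any interval shorter than planned, and report interval and cumulative dose with the safety data.

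The cost is one protocol amendment and one REDCap field for the reason, with no extra subjects or visits. The downside is that the label-consistency statement may have to be weakened.

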#### **5.3 Method for Assigning Subjects to Treatment Groups**

Subjects will be randomized to intervention or standard care using a random number generator with randomly permuted blocks, in blocks of 2, 4, and 6 subjects. Randomization is embedded and performed within the secure REDCap software electronically. After subjects have provided their informed consent to

CONFIDENTIAL

This material is the property of the NYU School of Medicine and Langone Medical Center. Do not disclose or use except as authorized in writing by the study sponsor

participate in the study, are determined to be eligible for it, and have completed all baseline assessments, the RA or PI will click on the randomization button in REDCap for the treatment assignment.

## 5.4 Preparation and Administration of Study Drug

Extended-release naltrexone (XR-NTX, VIVITROL) dose at 380mg (4 mL) will be administered as an intramuscular gluteal injection. XR-NTX (VIVITROL) will be prepared and administered by a healthcare professional (trained physician, physician assistant, or registered nurse) using aseptic technique at the FDA approved dosage using recommended administration techniques detailed below.

The PI has been carefully trained on the proper techniques of medication administration, including in his role as medical clinician for the National Institute on Drug Abuse Clinical Trials Network #0048 CURB study (August 2011). Any provider administering XR-NTX to study subjects will receive training as well. The PI will provide training personally and has access to supplemental webinar training resources as part of his membership in the National Institute on Drug Abuse Clinical Trials Network. Providers administering XR-NTX may include physicians, physician assistants, and registered nurses.

The entire carton should be stored in the refrigerator (2-8 °C, 36-46 °F). Unrefrigerated, XR-NTX (VIVITROL) Microspheres can be stored at temperatures not exceeding 25 °C (77 °F) for no more than 7 days prior to administration. Do not expose unrefrigerated product to temperatures above 25 °C (77 °F). XR-NTX (VIVITROL) should not be frozen.

Parenteral products should be visually inspected for particulate matter and discoloration prior to administration.

1. Remove the carton from refrigeration. Prior to preparation, allow drug to reach room temperature (approximately 45 minutes).
2. To ease mixing, firmly tap the XR-NTX (VIVITROL) Microspheres vial on a hard surface, ensuring the powder moves freely.
3. Remove flip-off caps from both vials. DO NOT USE IF FLIP-OFF CAPS ARE BROKEN OR MISSING.
4. Wipe the vial tops with an alcohol swab.
5. Place the 1 inch preparation needle on the syringe and withdraw 3.4 mL of the diluent from the diluent vial. Some diluent will remain in the diluent vial.
6. Inject the 3.4 mL of diluent into the XR-NTX (VIVITROL) Microsphere vial.
7. Mix the powder and diluent by vigorously shaking the vial for approximately 1 minute. Ensure that the dose is thoroughly suspended. A PROPERLY MIXED SUSPENSION WILL BE MILKY WHITE, WILL NOT CONTAIN CLUMPS, AND WILL MOVE FREELY DOWN THE WALLS OF THE VIAL.
8. Immediately after suspension, withdraw 4.2 mL of the suspension into the syringe using the same preparation needle
1. Select the appropriate needle for an intramuscular injection based on subject's body habitus:
  - a. 1.5 inch TERUMO® Needle
  - b. 2 inch NEEDLE-PRO® Needle
2. Remove the preparation needle and replace with appropriately selected administration needle for immediate use.
3. Peel the blister pouch of the selected administration needle open halfway. Grasp sheath using the plastic pouch. Attach the luer connection to the syringe with an easy clockwise twisting motion.
4. Seat the needle firmly on the needle protection device with a push and clockwise twist.
5. Pull the sheath away from the needle - do not twist the sheath because it could result in loosening the needle.
6. Prior to injecting, tap the syringe to release any air bubbles, then push gently on the plunger until 4 mL of the suspension remains in the syringe. THE SUSPENSION IS NOW READY FOR IMMEDIATE ADMINISTRATION.
7. Administer the suspension by deep intramuscular (IM) injection into a gluteal muscle, alternating buttocks per monthly injection. Remember to aspirate for blood before injection.

CONFIDENTIAL

This material is the property of the NYU School of Medicine and Langone Medical Center. Do not disclose or use except as authorized in writing by the study sponsor

8. If blood aspirates or the needle clogs, do not inject. Change to the spare needle provided in the carton and administer into an adjacent site in the same gluteal region, again aspirating for blood before injection.
9. Inject the suspension in a smooth and continuous motion. XR-NTX (VIVITROL) must NOT be given intravenously or subcutaneously.
10. After the injection is administered, cover the needle by pressing the needle protection device against a flat surface using a one-handed motion away from self and others. Visually confirm needle is fully engaged into the needle protection device. DISPOSE OF USED AND UNUSED ITEMS IN PROPER WASTE CONTAINERS.

